### **3.3.5. Imputation of Incomplete Dates**

A missing date is one in which the day, month or year are all unknown. For adverse events, if a date is missing entirely then the date will be set to equal Day 1.

An incomplete date is any date for which either the day, month or year is unknown, but all three fields are not unknown. An incomplete date occurs when the exact date an event occurred or ended cannot be obtained from a subject. For many of the analyses, a complete date is necessary to determine if the event should be included in the analysis (i.e., if the event is treatment-emergent). In such cases, incomplete dates will be imputed.

To minimize bias, the project statistician will impute dates in a systematic, but reasonable manner. If the month/year is the same as the Day 1 month/year, then the date will be set to the date of Day 1. In other cases, missing days will be imputed as the day component of Day 1; missing months/years will be imputed as the month/year of Day 1. For nonexistent dates occurring at the end of a month created by this imputation method, the first date of the next month will be used (e.g. Day 1 = 31JAN2017, incomplete date = XXFEB2017 -> imputed date = 01MAR2017).

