Adverse events will be coded with the Medical Dictionary for Regulatory Activities (MedDRA) and WHO Drug Global B3 March 2021. Treatment-emergent adverse events (TEAEs) are defined as AEs with an onset date on or after the date of first administration of study treatment and before the date of last administration of study treatment + 30 days. Treatment-emergent adverse events will be presented by system organ class and preferred term in frequency tables. Patients with multiple AEs will be counted only once within each preferred term and system organ class. Key patient information for patients with an AE with an outcome of death, patients with SAEs, and patients with an AE leading to discontinuation of study treatment will be listed.

Laboratory data (hematology, serum chemistry, coagulation, and urinalysis) will be converted to Système International (SI) units for reporting and processing purposes. Absolute values and changes from Baseline will be presented descriptively. Laboratory data outside study specific reference ranges will be listed. Vital signs and ECG parameters will be presented descriptively.

ATI-450 Drug Concentrations and Pharmacokinetic Analyses

Plasma concentrations of ATI-450 and its primary circulating metabolite, CDD-2164, will be summarized by day and sample. Concentration versus time since dose (Days 1, 8, 15, 29, 43, 57, and 85) will be displayed by linear scale.

Handling of Missing Data

[figure not shown]
Missing data will not be imputed for the safety summaries, or the efficacy summaries conducted on the PP population. All efficacy analyses conducted on the FAS population will use a last observation carried forward (LOCF) imputation. Additionally, a sensitivity analysis will be conducted for categorical endpoints conducted on the FAS using a non-responder imputation method. Further details regarding the imputation of data that are missing or following intercurrent events will be provided in the SAP.

Data Monitoring Committee:

An independent DSMB will convene to monitor interim safety data. Details regarding DSMB membership, responsibilities, and meeting frequency are outlined in the DSMB Charter.

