8.3.1 Time Period and Frequency for Collecting AE and SAE Information

All AEs and SAEs will be collected at the time points specified in the SoA ([Table 1](#)). Serious AE reporting will start at the time of consent. Any AE that occurs between the time of consent and prior to dosing on Day 1 will be recorded as medical history. All TEAEs will be collected following the first dose of study treatment on Day 1 through the Follow-up Visit (30 days after the last administration of study treatment).

All SAEs will be recorded and reported to the Sponsor/designee within 24 hours, as indicated in [Appendix 4](#). The Investigator will submit any updated SAE data to the Sponsor within 24 hours of it being available.

Investigators are not obligated to actively seek AEs or SAEs after conclusion of the study participation. However, if the Investigator learns of any SAE, including a death, at any time after a patient has been discharged from the study, and he/she considers the event to be reasonably related to the study treatment or study participation, the Investigator must promptly notify the Sponsor/designee.

The method of recording, evaluating, and assessing causality of AE and SAE and the procedures for completing and transmitting SAE reports are provided in [Appendix 4](#).

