9.4.2 Safety Analyses

The Safety population will be used for the analysis of safety data (AEs, exposure to study treatment, clinical laboratory values, vital signs, and ECG).

Adverse events will be coded with MedDRA and WHODrug Global B3 March 2021. The TEAEs are defined as AEs with an onset date on or after the date of first administration of study treatment and before the date of last administration of study treatment +30 days. Treatment-emergent adverse events will be presented by system organ class and preferred term in frequency tables. Patients with multiple AEs will be counted only once within each preferred term and system organ class. Key patient information for patients with an AE with an outcome of death, patients with SAEs, and patients with an AE leading to discontinuation of study treatment will be listed.

Laboratory data (hematology, serum chemistry, coagulation, and urinalysis) will be converted to Système International units for reporting and processing purposes. Absolute values and changes from Baseline will be presented descriptively. Laboratory data outside study specific reference ranges will be listed. Vital signs and ECG parameters will be presented descriptively.

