Dermatology Life Quality Index (DLQI)

The DLQI is calculated by summing the score of each question resulting in a maximum of 30 and a minimum of 0. The higher the score, the more quality of life is impaired. If one question is unanswered, this is allocated a score of 0 for the purpose of summing to the DLQI score. If two or more questions are unanswered, the questionnaire is not scored.

Each question is answered on a Likert scale: Very much=scored 3, A lot=scored 2, A little= scored 1, Not at all= scored 0, Not relevant=scored 0, Question Not Answered=0. Question 7 is asked in two parts. The first part asks if the skin disease has ‘prevented you from working or studying’. If skin disease has prevented working or studying, then Question 7 is scored 3. If working or studying are not relevant, the response is Not relevant and scored 0. If the answer is No, then Question 7 is scored based on the second part of the question as to ‘How much has your skin been a problem at work or studying’: ‘A lot’(scored 2), ‘A little’ (scored 1) or ‘Not at all’ (scored 0).

Treatment-Emergent Adverse Event (TEAE)

TEAEs are defined as AEs with an onset date on or after the date of first administration of study drug and before the date of last administration of study drug + 30 days.

Treatment-Emergent Laboratory Abnormalities

A treatment-emergent laboratory abnormality is defined as a result in which the baseline value is within normal laboratory limits and the post-baseline value is outside normal laboratory limits. If the relevant baseline assessment is missing, then any post-baseline value outside normal laboratory limits will be considered a treatment-emergent value.

Treatment-emergent Laboratory Toxicity

A treatment-emergent laboratory toxicity is defined as an increase of at least one toxicity grade from the baseline assessment at any post baseline visit. If the relevant baseline assessment is missing, then any graded abnormality (i.e., at least Grade 1) is considered to be treatment-emergent.

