#### **5.5.1. Adverse Events**

Adverse events (AE) will be mapped to a PT and system organ classification (SOC) using MedDRA version 24.0.

An overall summary will be presented which includes the number of TEAEs and the number and percentage of patients who experienced at least one TEAE. This summary will also include:

- Any TEAE
- Any Serious TEAE
- Any Mild TEAEs
- Any Moderate TEAEs
- Any Severe TEAEs
- Any Related TEAEs (defined as Probably or Possibly Related)
- Any TEAEs leading to discontinuation of study drug
- Any Related TEAEs leading to discontinuation of study drug

- Commonly occurring TEAEs (defined as those AEs occurring in  $\geq 10\%$  of ATI-450 patients)

Adverse events of special interest (AESI) are captured on the AE eCRF page and include the following events: mouth ulceration, severe skin reaction which is considered to be related to the study drug, confirmed creatine kinase (CK)  $> 5X$  ULN without benign explanation, absolute neutrophil count  $< 1000$  cells/mm^3, and QTcF  $> 500$  msec or change from baseline QTcF  $> 60$  msec.

Additional summaries of TEAEs will be provided showing the number and percentage of patients who experienced at least one TEAE. These summaries will be presented by SOC and PT. If a participant reports the same PT multiple times within the same SOC, that PT will only be counted once within that SOC for that participant. As with the PT, if a participant reports multiple conditions within the same SOC, that SOC will only be counted once for that participant. In the summary, SOC will be listed in ascending alphabetical order; PTs will be listed in order of descending frequency for all participants within each SOC.

The occurrence of TEAEs related to study medication, TEAEs leading to discontinuation of study drug, study drug related TEAEs leading to discontinuation, AESIs, and serious adverse events (SAEs) will be tabulated by SOC and PT. An additional summary of TEAEs will be provided by SOC, PT and maximum severity. Most frequent TEAEs, defined as AEs occurring in 10% of ATI-450 patients, will be summarized by PT.

All AEs reported will be listed by individual subject, showing both verbatim and PT. All AEs reported with a start date prior to the initiation of study medication will be excluded from the TEAE tables but will be included in the listings.

Missing onset dates will be imputed as previously outlined in [Section 3.3.5](#) as required to determine TEAEs.

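### The partial-date rule for adverse events has no check at the end of the TEAE window, so some in-window events drop out of the TEAE tables; the window also excludes day + 30 after last dose

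*SAP*

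**What the plan says.** **Imputation.** SAP 3.3.5 treats AE onset dates in three ways:
- No part of the date known: "For adverse events, if a date is missing entirely then the date will be set to equal Day 1".
- Month and year equal to those of Day 1: the date becomes Day 1.
- Any other partial date: "missing days will be imputed as the day component of Day 1; missing months/years will be imputed as the month/year of Day 1". If this produces a date that does not exist, the first of the following month is used.

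**Use.** In SAP 5.5.1, "Missing onset dates will be imputed as previously outlined in" SAP 3.3.5, for the purpose of identifying TEAEs.

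**Window.** SAP 3.3.8 defines a TEAE as an AE with onset on or after first dose and "before the date of last administration of study drug + 30 days". Protocol 9.4.2 ("before the date of last administration of study treatment +30 days") and the Protocol synopsis ("before the date of last administration of study treatment + 30 days") agree.

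**Collection.** Protocol 8.3.1 says TEAEs are collected "through the Follow-up Visit (30 days after the last administration of study treatment"). Footnote h of the schedule of assessments says the same in both documents.

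**The concern.** The rule protects one end of the window only. A partial date in the Day 1 month is pulled to Day 1 and so counts. At the other end, the day-of-month of Day 1 is inserted without checking it against last dose + 30 days. An event that began inside the window can therefore be dated beyond it and leave the TEAE tables because of the calendar day on which the patient started treatment.

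The result is also out of line with the rest of the SAP. An AE with no date at all is set to Day 1 and counted, and under SAP 3.3.4 a missing relationship counts as related and a missing severity as severe. Yet knowing part of a date can remove an event that knowing nothing would keep.

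The boundary is a separate, smaller point. An onset exactly 30 days after last dose falls within the stated collection period for TEAEs but fails the TEAE definition.

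What is at stake is the completeness of the TEAE tables. No bias between arms is claimed, because the rule is the same in both. No particular claim is made about serious AEs either: the text of SAP 5.5.1 says "AESIs, and serious adverse events (SAEs) will be tabulated by SOC and PT" without limiting these to TEAEs, although the title of Table 14.3.1.4 does limit the SAE table.

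**Working it through.** **Inputs.** The date rule is from SAP 3.3.5 and the window from SAP 3.3.8. A completer's last dose is on Day 85, that is Day 1 + 84 (schedule footnote g). The follow-up visit is at 30 days with a tolerance of + 7.

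**The SAP's own example.** Day 1 = 31 Jan 2017 and onset in Feb 2017, day unknown. There is no 31 Feb, so the date becomes 1 Mar 2017, as the SAP states.

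**Day missing, one case.** Day 1 = 20 Mar 2022; last dose = Day 1 + 84 = 12 Jun; last dose + 30 = 12 Jul. An AE recorded as Jul 2022 is dated 20 Jul. It is not a TEAE even if it began on 1 Jul.

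**Day missing, all cases.** Take each of the 365 Day 1 dates in 2022 and each possible onset day, delete the day, apply the rule, and test for a date earlier than last dose + 30. For completers the denominators are 365 × 85 = 31,025 on treatment, 365 × 29 = 10,585 at + 1 to + 29, and 365 × 114 = 41,610 in all.

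| Completers, onset | Lost | Share |
|---|---|---|
| On treatment | 0 / 31,025 | 0% |
| + 1 to + 7 | 5 / 2,555 | 0.2% |
| + 8 to + 14 | 315 / 2,555 | 12.3% |
| + 15 to + 21 | 903 / 2,555 | 35.3% |
| + 22 to + 29 | 1,752 / 2,920 | 60.0% |
| + 1 to + 29 | 2,975 / 10,585 | 28.1% |
| Whole window | 2,975 / 41,610 | 7.1% |

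Of the 365 Day 1 dates, 261 are affected. With Day 1 in 2023 the + 1 to + 29 loss is 2,929 / 10,585 = 27.7%.

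For patients who stop early, the loss depends on the last-dose day:

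| Last dose | Lost at + 1 to + 29 | Share of whole window |
|---|---|---|
| Day 15 | 1,030 / 10,585 = 9.7% | 1,030 / 16,060 = 6.4% |
| Day 29 | 4,404 / 10,585 = 41.6% | 4,404 / 21,170 = 20.8% |
| Day 43 | 686 / 10,585 = 6.5% | 686 / 26,280 = 2.6% |
| Day 57 | 3,654 / 10,585 = 34.5% | 3,654 / 31,390 = 11.6% |

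No on-treatment onset is lost in these four cases. Over every last-dose day from 1 to 85, only 19 of the 2,233,800 combinations enumerated lose an on-treatment onset.

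**Only the year known, completers.** Day 1 = 1 Nov 2022, last dose 24 Jan 2023. An AE recorded as 2023 becomes 1 Nov 2023, which is 365 − 84 = 281 days after last dose, even if it began on treatment on 10 Jan. The same happens to every in-window onset in the year after Day 1. This can arise for 113 Day 1 dates (10 Sep to 31 Dec), giving 1 + 2 + … + 113 = 113 × 114 / 2 = 6,441 onset days, all lost. On-treatment onsets are reached for 84 Day 1 dates (9 Oct to 31 Dec): 84 × 85 / 2 = 3,570, all lost.

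**Boundary.** Day 85 + 30 = Day 115. An onset on Day 115 is not before Day 115, so it is excluded. With exact dates, that one day is the whole mismatch.

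**Changing the word alone.** With *on or before* and the present imputation, 3,248 of 10,950 day-missing onsets at + 1 to + 30 are still lost (29.7%).

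**Earliest-date rule.** Lost: 0 / 41,610 with the present cut-off and 0 / 41,975 with *on or before*. For year-only dates, 0 / 6,441.

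**The case against.** - **Size.** The rule acts only on dates still partial at database lock. The documents give no rate, and the AE recording rules in Protocol Appendix 4 are not available here. Visits are frequent and investigators follow events from visit to visit. *This stands:* the percentages are shares of possible calendar days, not of expected events.
- **On-treatment events.** With only the day missing, the losses are essentially all off drug. *This stands.* For early discontinuers the whole-window shares are the fairer headline, and both are shown.
- **Year-only dates.** They should be rare in a 12-week trial. The wording could also be read as replacing month and year together with those of Day 1, which would keep the event. *The rarity stands. The reading does not,* because it would overwrite a year that is known.
- **Boundary.** Collecting for a day beyond an analysis window is not in itself a contradiction. *This stands in part:* it is one off-drug day. But Protocol 8.3.1 and footnote h describe what is collected up to then as treatment-emergent, and the definition excludes it. The + 7 visit tolerance does not by itself make later onsets TEAEs.
- **Remedy.** It counts more onsets from outside the window. Adding lost and wrongly counted onsets, with the present cut-off and visits at the + 37 maximum, total misclassification rises for last dose Day 15 (1,030 + 1,280 = 2,310 to 2,488) and Day 43 (686 + 1,512 = 2,198 to 2,488). It falls for Day 85 (2,975 + 403 = 3,378 to 2,488), Day 29 and Day 57. *This stands as a cost.* Over-inclusion is the more cautious error in a safety table, and it matches how the SAP treats wholly missing dates.

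**Conclusion.** Both parts hold on the text as written, at minor severity. SAP 3.3.5 can move an in-window AE out of the TEAE tables. For completers with only the day missing, this affects 28.1% of possible onset days at + 1 to + 29, 7.1% of the whole window, and none on treatment. A year-only date in the year after Day 1 is always lost, including on-treatment onsets. The TEAE definition also omits day + 30.

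These shares assume Day 1 dates spread evenly over 2022 and give every onset day equal weight. The number of AEs affected depends on how many partial dates remain, which is unknown, and is probably small. Efficacy is untouched and every AE stays in the listings.

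**What to change.** 1. **SAP 3.3.5, partial AE onset dates only.** Replace the rule with: impute the earliest date consistent with the known parts that is not before first dose and not after the AE stop date; if no such date exists, the event is not treatment-emergent. An event then counts unless the known parts rule it out.
2. **SAP 3.3.8, Protocol 9.4.2 and the Protocol synopsis.** Change *before* to *on or before* last dose + 30 days. All three places should change together so that the documents stay consistent.

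Both changes are needed, since the second does not repair the dating problem. The edit is one sentence in the SAP and one word in three places.

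The cost is over-inclusion, shown here for completers with the day missing:
- Present cut-off: 2,488 / 2,920 (85.2%) of onsets at + 30 to + 37 would be counted, against 403 / 2,920 (13.8%) now.
- With *on or before*: 2,219 / 2,555 (86.8%) of onsets at + 31 to + 37, against 311 / 2,555 (12.2%) with the present imputation.

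A known stop date does not lower these figures but prevents impossible dates. Extending the window to the actual follow-up visit (at most + 37) is optional and would make time at risk unequal between patients.

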### **3.3.6. Imputation of Alphanumeric Data**

Should there be instances where a clinical laboratory parameter is reported with imbedded non-numeric characters, as for example, “<0.1” or “>10”, the data will be imputed for the purpose of quantitative summaries. The actual values as reported in the database will be presented in data listings.

For incorporation in quantitative summaries, the following imputation rules will be employed:

The lower limit of quantification will be replaced with ½ the value of the lower limit. For example, “< 0.1” will be imputed as “0.05”.

The upper limit of quantitation will be increased by one level of precision that precedes the value. For example, “>0.1” will be imputed as “0.11”, and “>10” will be imputed as “10.1”.

---

Results reported as “ $\geq X$ ” and “ $\leq X$ ” will be imputed as “X”.

**3.3.7.** [REDACTED]

[REDACTED]

[REDACTED]

[REDACTED]

**3.3.8. Definitions and Terminology**

**Duration of HS (years)**

(Date of informed consent minus the start date of the HS +1)/365.25.

The start date of the HS is collected as part of Medical History and based on the Medical Dictionary for Regulatory Activities (MedDRA) coded preferred term of ‘Hidradenitis suppurativa’.

**Baseline Value**

For purpose of analysis, the baseline value is defined as the last non-missing value obtained prior to initiation of study drug. For assessments occurring on the date of first administration of study drug, if time of collection is reported, the time will be used to determine if the assessment occurred prior to initiation of study drug. If collection time is not reported, then the assessment will be assumed to be prior to initiation of study drug.

**Study Day**

Study Day is defined relative to Day 1, where Day 1 is the day of date of first dose as reported on the Dosing Diary eCRF. Thus, the study day of an event is calculated as:

Study Day = ((event date – date of Day 1) + 1) for dates on or after Day 1

Study Day = (event date – date of Day 1) for dates prior to Day 1

**Last Dose of Study Drug**

Last Dose of Study Drug is defined as the date of last dose taken as recorded on eDiary page of the eCRF.

**Study Drug Exposure (days)**

Study drug exposure is defined as: ((date of last dose of study drug – date of Day 1) + 1).

**Dose Interruptions**

Dose interruption is defined as  $\geq 2$  consecutive days where the subject missed both doses of the study drug as determined by the date and time fields on the eDiary page of the eCRF.

---

Study drug compliance (%) based on number of doses

Compliance (%) = (number of doses taken / number of doses that should have been taken) x100.

- The number of doses taken is calculated as: [day 1 dose + sum of number of doses taken as indicated on the eDiary CRF].
- The number of doses that should have been taken is calculated as: (2 \* study drug exposure days).

Prior Medications

Prior medications are those medications taken prior to the initiation of study medication, regardless of whether it continues into the blinded treatment period.

Concomitant Medications

Concomitant medications are those medications taken on or after the initiation of study medication through the end of treatment date minus 1. This definition includes medications started prior to the initiation of study medication but continued concomitantly with the study medication.

Change from Baseline

Change from Baseline for a given endpoint is defined as the value at the analysis visit minus the baseline value.

Percent Change from Baseline

Percent Change from Baseline for a given endpoint is defined as the value at the analysis visit minus the baseline value, quantity divided by the baseline value.

Hidradenitis Suppurativa Clinical Response (HiSCR50) Achiever

To meet the HiSCR50 criteria for achiever, the patient must have  $\geq 50\%$  reduction from baseline in the total abscess and inflammatory nodule (AN) count, have no increase in the number of abscesses from baseline, and have no increase in the number of draining fistula counts. A patient is considered an achiever only if all 3 criteria are fulfilled.

NRS30 Achiever

To meet the NRS30 criteria for achiever, the patient must have  $\geq 30\%$  reduction from baseline in PGA-SP and at least 1 unit reduction from baseline in the PGA-SP. This is assessed in patients with Baseline PGA-SP  $\geq 3$ .

International Hidradenitis Suppurativa Severity Score System (IHS-4)

The IHS-4 score (points) = (number of nodules multiplied by 1) + (number of abscesses multiplied by 2) + [number of draining tunnels (fistulas/sinuses) multiplied by 4].

Interpretation of the IHS-4 is as follows: mild HS is a score of 3 or less, moderate HS is a score of 4-10, and severe HS is a score of 11 or higher.

Dermatology Life Quality Index (DLQI)

The DLQI is calculated by summing the score of each question resulting in a maximum of 30 and a minimum of 0. The higher the score, the more quality of life is impaired. If one question is unanswered, this is allocated a score of 0 for the purpose of summing to the DLQI score. If two or more questions are unanswered, the questionnaire is not scored.

Each question is answered on a Likert scale: Very much=scored 3, A lot=scored 2, A little= scored 1, Not at all= scored 0, Not relevant=scored 0, Question Not Answered=0. Question 7 is asked in two parts. The first part asks if the skin disease has ‘prevented you from working or studying’. If skin disease has prevented working or studying, then Question 7 is scored 3. If working or studying are not relevant, the response is Not relevant and scored 0. If the answer is No, then Question 7 is scored based on the second part of the question as to ‘How much has your skin been a problem at work or studying’: ‘A lot’(scored 2), ‘A little’ (scored 1) or ‘Not at all’ (scored 0).

Treatment-Emergent Adverse Event (TEAE)

TEAEs are defined as AEs with an onset date on or after the date of first administration of study drug and before the date of last administration of study drug + 30 days.

Treatment-Emergent Laboratory Abnormalities

A treatment-emergent laboratory abnormality is defined as a result in which the baseline value is within normal laboratory limits and the post-baseline value is outside normal laboratory limits. If the relevant baseline assessment is missing, then any post-baseline value outside normal laboratory limits will be considered a treatment-emergent value.

Treatment-emergent Laboratory Toxicity

A treatment-emergent laboratory toxicity is defined as an increase of at least one toxicity grade from the baseline assessment at any post baseline visit. If the relevant baseline assessment is missing, then any graded abnormality (i.e., at least Grade 1) is considered to be treatment-emergent.

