AE=adverse event; AN=abscess and inflammatory nodule count; BMI=body mass index; DLQI=Dermatology Life Quality Index; ECG=electrocardiogram; EOS=end of study; ET=early termination; HIV=human immunodeficiency virus; HS=hidradenitis suppurativa; hsCRP=high sensitivity C-reactive protein; HS-PGA=Physician Global Assessment Scale; mRNA=messenger RNA; NRS30= Numerical Rating Scale for Patient's Global Assessment of Skin Pain; PD=pharmacodynamic; PK=pharmacokinetic; SARS-CoV-2=severe acute respiratory syndrome coronavirus 2; TB=tuberculosis; WOCBP=women of childbearing potential.

[figure not shown]
- a. Triplicate 12-lead ECGs will be performed at least 30 seconds apart, in a supine position, after resting for at least 10 minutes (without external stimulation, e.g., talking, TV, noise) and submitted for central reading. Screening ECGs will be collected prior vital signs and blood samples. On Day 1 and 8, ECGs will be taken predose and 2 hours postdose. Patients not fasting on Day 1 and 8 will have an additional 4 hr postdose ECG. On Days 15, 29, 43, 57, and 85 ECGs will be performed as the last assessment in the clinic (as close to Cmax). See [Section 8.2.3](#) for additional details on collection parameters.
- b. Vital signs are to be taken before blood collection for laboratory tests. See [Section 8.2.2](#) for additional details on collection parameters.
- c. PK blood sampling times on Days 1, 8, and 85 will occur predose and 2 hours after the morning dose. Patients not fasting on Days 1 and 8 will have an additional PK sample collected at 4 hours postdose. If the patient objects to both blood draws at the 2hr and 4hr timepoint, the 4hr PK sample is more important to collect. Patients must remain in the clinic until 30 minutes after the morning postdose PK blood sampling is completed. See [Section 8.5](#) for additional details on collection parameters.
- d. PK blood sampling will occur prior to the morning dose on Days 15, 29, 43, and 57. See [Section 8.5](#) for additional details on collection parameters.
[REDACTED]
[REDACTED]
[REDACTED]
- g. The last dose of study treatment will be administered in the clinic on Day 85. The second dose of study treatment is not to be administered on Day 85.

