6.4 Study Treatment Compliance

The prescribed dosage, timing, and mode of administration may not be changed. Any departures from the intended regimen must be recorded in the eCRFs.

At each visit, prior to dispensing study treatment, previously dispensed study treatment will be retrieved by the Investigator and compliance assessed both through tablet counting and review of a dosing diary completed by the patient. Patients exhibiting poor compliance as assessed by tablet counts and diary completion should be counseled on the importance of good compliance to the study dosing regimen.

Noncompliance is defined as taking <80% or >120% of study treatment during any evaluation period (visit to visit). See [Section 8.4](#) regarding treatment of ATI-450 overdose.

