7.2 Temporary Discontinuation

7.2.1 Unrelated Adverse Events or COVID-19 Diagnosis

If a drug is stopped temporarily due to a clearly unrelated adverse event, for example, treatment of a fracture caused by a motor vehicle accident or COVID-19 infection, dosing may be reinitiated, after discussion with the Medical Monitor, if the temporary discontinuation was shorter than a maximum of 14 days in the total 12-week treatment period. In exceptional circumstances, medical monitor may allow dosing to be resumed with a gap of up to 21 days. In all cases, if the dosing gap is in excess of 21 days, dosing should be discontinued permanently.

In case of a COVID-19 infection, consult study Medical Monitor to discuss risk/benefit considerations of patient continuing or discontinuing study medication treatment.

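### SAP 3.3.8 computes one whole-exposure compliance percentage and does not implement the protocol's visit-to-visit definition of noncompliance; separately, its expected-dose count is one too high for a Day 85 completer

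*SAP*

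**What the plan says.** Protocol 6.4 has returned study drug collected at each visit, with "compliance assessed both through tablet counting and review of a dosing diary completed by the patient". It then sets the limit: "Noncompliance is defined as taking <80% or >120% of study treatment during any evaluation period (visit to visit".

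SAP 3.3.8 defines one ratio per patient: "Compliance (%) = (number of doses taken / number of doses that should have been taken) x100". The numerator is the Day 1 dose plus the doses recorded on the eDiary CRF. The denominator is given as: "The number of doses that should have been taken is calculated as: (2 \* study drug exposure days". Exposure runs from Day 1 to the last dose date, inclusive, and "Last Dose of Study Drug is defined as the date of last dose taken as recorded on eDiary page of the eCRF". No interval, threshold or compliant/noncompliant category is stated. The same section defines a dose interruption as at least 2 consecutive days on which both doses were missed.

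SAP 5.3 and Table 14.1.3 summarise treatment duration, interruptions and compliance. Diary data and tablet counts go to listings only.

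Footnote g of the schedule of assessments, which the SAP repeats, says of the final treatment day: "The second dose of study treatment is not to be administered on Day 85". Protocol 7.2.1 allows temporary holds and adds: "In exceptional circumstances, medical monitor may allow dosing to be resumed with a gap of up to 21 days".

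**The concern.** The protocol's rule asks whether any single interval was bad. The SAP's percentage averages over all intervals, so one poor interval is diluted by the good ones, and under-use in one interval can offset over-use in another. Table 14.1.3 is where a reader will look to see whether patients took 50 mg BID. The longest interval, Days 57-85, comes immediately before the Week 12 lesion count on which the primary endpoint rests, and it is there that the average can hide the most missed doses.

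SAP 4.2 has the sponsor judge, blinded, which major deviations could affect efficacy. An interval-level compliance flag is an obvious input to that review, although neither document says that compliance is used there.

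The denominator also conflicts with the dosing schedule on Day 85, and the numerator does not make clear which doses the eDiary sum already contains.

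**Working it through.** The plan gives no compliance figure to reproduce, so the check is a dose count. Assumptions: visits on the nominal days (1, 8, 15, 29, 43, 57, 85), two doses on each of Days 1-84, and one dose on Day 85.

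**Expected doses for a completer**
- From the schedule: 2 x 84 + 1 = 169.
- From the SAP: 2 x (85 - 1 + 1) = 170.
- By interval (2 x days between visits): 14 + 14 + 28 + 28 + 28 + 56 = 168, plus the Day 85 morning dose = 169.

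**Masking.** For each interval, take the largest dose count that is still below 80%, with perfect intake elsewhere:

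| Interval | Expected | Taken | Interval % | SAP overall |
|---|---|---|---|---|
| Days 1-8 or 8-15 | 14 | 11 | 78.6 | 166/170 = 97.6% |
| Days 15-29, 29-43 or 43-57 | 28 | 22 | 78.6 | 163/170 = 95.9% |
| Days 57-85 | 56 | 44 | 78.6 | 157/170 = 92.4% |

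- Just below 80% in all of the first five intervals: 3 + 3 + 6 + 6 + 6 = 24 doses missed, and (169 - 24)/170 = 85.3%.
- Cancellation: 22/28 (78.6%) in one interval and 34/28 (121.4%) in another gives (169 - 6 + 6)/170 = 99.4%, the same as perfect intake.
- What the interruption summary sees: if the 12 doses missed in Days 57-85 are 12 single evening doses, no day has both doses missed and nothing is reported. If they are 6 consecutive full days, an interruption is reported.

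**Day 85 error**
- Perfect intake scores 169/170 = 99.4%, which is 0.6 point too low.
- Correcting the denominator moves the 44/56 patient only from 92.4% to 157/169 = 92.9%. The averaging, not the denominator, hides the bad interval.
- If an 80% limit were applied overall, no Day 85 completer would change sides: 0.8 x 170 = 136 and 0.8 x 169 = 135.2, so the smallest passing count is 136 either way. At 120% only totals of 203 or 204 doses would change (1.2 x 169 = 202.8; 1.2 x 170 = 204).

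**Numerator.** SAP 3.3.8 says that "Day 1 is the day of date of first dose as reported on the Dosing Diary eCRF".
- If that dose is also in the eDiary sum, it is counted twice and a perfect completer scores 170/170 = 100%.
- If clinic doses are not in the eDiary, the six later clinic morning doses (Days 8, 15, 29, 43, 57, 85) drop out, leaving 169 - 6 = 163. The last eDiary dose then falls on Day 84, the denominator becomes 2 x 84 = 168, and the score is 163/168 = 97.0%.
- The last dose date is taken from the eDiary, and the last dose is scheduled in clinic on Day 85. This suggests that at least that clinic dose is recorded there, but the eCRF layout is not shown and the point stays open.

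**Holds.** A 21-day hold with otherwise perfect intake gives (169 - 42)/170 = 74.7%. In this percentage it looks the same as a patient who missed 42 doses unprompted.

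**The case against.** The strongest reply is that 6.4 is a rule for sites. Its stated consequence is counselling, no protocol analysis uses it, and the per-protocol definition does not name compliance. On that view an overall percentage breaches nothing. Dosing is also visible elsewhere: interruptions are summarised beside compliance, deviations are tabulated in Table 14.1.1.4, diary and tablet counts are listed, and plasma ATI-450 is sampled at every treatment visit. SAP section 6, on changes from the protocol, is blacked out in the public copy and may address the point.

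Much of this stands and limits the importance of the point. It does not remove it. The interruption rule misses scattered doses, PK samples inform only on dosing around visits, and deriving an interval measure later from listings would mean choosing the rule after the fact. The protocol has already set a definition, and the planned table does not report it.

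Three stronger readings are tempting, and the documents do not support them:
- A reader might infer that noncompliant patients will be reported as compliant. The SAP sets no such category; it reports a percentage.
- A reader might infer that the wrong expected-dose count hides noncompliance. It lowers the percentage by about 0.6 point.
- A reader might infer that the SAP overstates adherence throughout, so that a null result could not be told apart from under-dosing. The directions are mixed: averaging hides bad intervals, while the Day 85 dose and permitted holds lower the figure. The other sources of dosing evidence also remain.

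**Conclusion.** The point holds in a limited form. SAP 3.3.8 does not implement the protocol 6.4 definition, and a patient who is noncompliant in Days 57-85 can show 92.4% overall without being flagged in any planned table. The Day 85 denominator is a separate error of one dose in 170, in the direction of understating compliance. The Day 1 and eDiary sum is ambiguous: a perfect completer could score 100%, 99.4% or 97.0%, and the documents do not show which.

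The figures assume nominal visit days and a last dose on Day 85; the ±1 day visit window shifts them slightly. The effect is on how exposure is interpreted and possibly on per-protocol membership. The primary MMRM on the full analysis set does not change.

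**What to change.** In SAP 3.3.8 and 5.3:
- Derive compliance for each visit-to-visit interval as well as overall.
- Expect one dose on Day 85.
- Check the numerator against the eCRF layout so that each clinic and home dose is counted exactly once, and reconcile it with the tablet counts already collected.

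In Table 14.1.3, add the number and percent of patients who meet the protocol 6.4 definition in any interval, with protocol-permitted holds identified separately. Make the flag available to the blinded per-protocol review before database lock.

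The cost is SAP wording and some programming; diary, dosing and tablet-count data are already collected. The downside is that the table will show patients with noncompliant intervals that the overall percentage does not reveal.
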